9.10. Deviation Handling

The investigator must notify Medtronic and the reviewing IRB of any deviation from the protocol when specific to the protection of the life or physical well-being of a subject in an emergency. Such notice must be given as soon as possible, but in no event later than 5 working days after the emergency has occurred. Except in such an emergency, prior written approval by Medtronic is required for changes in or deviations from the plan. If these changes or deviations affect the scientific soundness of the plan or the rights, safety, or welfare of human subjects the IRB will also be notified. All other deviations will be reported per the site's IRB deviation policy. Should any deviations from the protocol occur, these will be reviewed by Medtronic for their clinical significance.

Protocol deviations identified by the Monitor during a monitoring visit should be discussed with the Principal Investigator/ Study staff involved at the time of discovery. Protocol non-compliance will be documented accordingly and communicated again in writing to the site within the follow-up letter. Monitors will also escalate the deviations significant in nature to the study manager (or designee), as soon as possible.

9.11. Subject Withdrawal or Discontinuation

Subjects will be considered to have completed the study after completion of the last study visit (followup phone call). Subjects may be withdrawn prior to this for any of the following reasons:

- Death, or
- Lost to follow-up, or
- Withdrawal of consent, or
- Discontinuation by the investigator.

COVB2710467

Documentation must be maintained at the site for any subject withdrawals. Subjects unable to complete Cytosponge administration will be withdrawn from the study (discontinued by investigator). Three attempts at contact using two different methods are required prior to determining the subject is lost to follow-up. Attempts at contact must be with certified letters OR documented telephone contact. If a subject is withdrawn prior to completion of the study, the site should complete the Study Exit e-CRF.

10. Risks and Benefits

10.1. Potential Risks

There are several possible risks that could occur when swallowing the Cytosponge capsule which include but are not limited to:

- Aspiration (accidentally inhaling material from the stomach into the lungs) and/or airway obstruction are possibilities but these risks are expected to be minimal.
- Although the sponge is soft, possible risks include, bleeding, pain, vomiting, sore/irritated throat, and burning sensation from any mucosal surfaces of the mouth, stomach or esophagus (swallowing tube) which comes in contact with the sponge.
- Laceration of any mucosal surface coming into contact with the sponge is possible, including mucosal surfaces of the stomach, esophagus, throat or mouth. Although very unlikely, perforation of the stomach or esophagus is also possible which could require secondary intervention.
- Although the risk has been found to be 2%, sponge detachment from the suture could also occur. Should this occur, the sponge will be retrieved during the planned endoscopy that follows administration of the sponge. Although not observed in previous Cytosponge studies the risk of infection or intestinal obstruction is a possibility.

The current study has been designed to minimize occurrence of these potential risks by use of the exclusion criteria. Most subjects enrolled in this study will have previously received an upper endoscopy, which will document the absence of esophageal varices and strictures. During administration of the sponge, the patient is not sedated and the device does not render the upper esophageal sphincter incompetent. These elements further reduce the overall risk for serious adverse events.

All serious adverse events, which, based on the investigator's judgment, are considered to be device related, should be reported to Medtronic-GI Solutions within 24 hours after the investigator is made aware of the event.

10.2. Potential Benefits

The study may allow Medtronic and the study doctors to assess whether this procedure can be an acceptable method of collecting a sample of cells from the lining of the esophagus.

This study will help in gathering information on the outcomes associated with the Cytosponge ™ Cell Collection Device and therefore might inform future decisions regarding this product and its indicated uses.

Version G 01-DEC-2017

COVB2710467

10.3. Risk-Benefit Rationale

Risk analysis for Cytosponge[™] Cell Collection Device was conducted in compliance with ISO14971. The overall evaluation of the residual system risks found no unacceptable hazards of significant impact to the safety and reliability of the Cytosponge[™] Cell Collection Device. The residual risks of the Cytosponge[™] Cell Collection Device, design, and process hazards were rated as BAR (Broadly Acceptable Region) or ALAP (As Low as Possible) in accordance with the risk acceptability criteria as documented in Risk Management Report

Based on the risk analyses per the SHA
 A the dFMEA
 A the pFMEA
 A the pFMEA
 A the sterile Cytosponge[™] Cell Collection Device (CYTO-101) have been reduced to acceptable level.

• Risks related to Secondary Intervention, Mucosal Laceration, Pre-Procedural Delay, Intra-Procedural Delay, Airway Obstruction, Unable to use sample for diagnosis, Infection, Minor Bleeding, Reaction due to non-Biocompatibility, Aspiration, Intestinal Obstruction and Dysphagia have been reduced to an acceptable level in BAR and/or ALAP-B risk regions for the Cytosponge[™] Cell Collection Device (CYTO-101).

- Future updates to design and/or process pertaining to these risks will be captured with the inclusion of updated risk controls as applicable.
- None of the risks fall in the intolerable region and the current risks are reduced and/or continually controlled via existing measures; the residual risks from current risks are deemed acceptable based on the implementation of existing risk controls.
- This report is applicable only to sterile and non-sterile Cytosponge[™] Cell Collection Device (CYTO-101) samples for intended use; performance/functionality testing was performed on e-beam sterilized samples since sterilization presents worst case processing/conditions as mentioned in performance testing for equivalency of non-sterile samples with sterile samples.
- Within this clinical trial, the benefits of using the Cytosponge[™] Cell Collection Device (CYTO-101) for the intended use outweigh the risks.

11. Adverse Events and Device Deficiencies.

11.1. Definitions/Classifications

Adverse event: any unwanted medical occurrence in a subject. An event is a sign, symptom, illness, abnormal laboratory value, or other medical event occurring to a subject that appears or worsens during a clinical study. Adverse events will be collected and documented after the subject has signed the

COVB2710467

Informed Consent form, until the completion of the final Cytosponge administration post-procedure 7-day phone call is completed; which will be considered to be the end of the study.

All adverse events will be graded as follows:

Mild: Sign or symptom, usually transient, requiring no special treatment and generally not interfering with usual activities.

Moderate: Sign or symptom, which may be ameliorated by simple therapeutic measures, may interfere with usual activity.

Severe: Sign or symptom that is intense or debilitating and that interferes with usual activities. Recovery is usually aided by therapeutic measures and the discontinuation of the study device may be required.

The relationship of the adverse event to the study is defined as follows:

No Relationship: An adverse event has no temporal relationship to study device or has a much more likely alternative etiology.

Possible: An adverse event has a minimal temporal relationship to the study device and/or a more likely alternative etiology exists.

Probable: An adverse event has a strong temporal relationship to study device, and an alternative etiology is unlikely or significantly less likely compared to the potential relationship to study device.

Definite: An adverse event was shown to be related to the study device.

Device Deficiency: Inadequacy of a medical device related to its identity, quality, durability, reliability, safety or performance such as a malfunction, misuse or use error or inadequate labeling.

Unknown: The relationship of the adverse event to the study device is inconclusive.

Adverse Event will be reported to Medtronic-GI Solutions utilizing the electronic case report (Adverse Event CRF eForm)

Adverse device effects: device related adverse events caused wholly or partly by the use of the device. A causal relationship between an observed adverse event and the use of the trial device may exist with various degrees of probability, on the basis of statistical probability, or of plausible medical data and considerations.

In the case of adverse device effect with the Cytosponge[™] Cell Collection Device, the Cytosponge capsule should be postponed until adverse device effect is resolved and per physician discretion.

Serious adverse event is any adverse event that:

- Led to death
- Resulted in a life-threatening illness or injury
- > Led to persistent or significant disability or incapacity
- > Required inpatient hospitalization or prolongation of existing hospitalization
- > Led to fetal distress, fetal death, congenital anomaly/birth defect.
- Resulted in medical or surgical intervention to prevent life threatening illness or permanent impairment to body structure or body function.
- > Other significant medical event.

Some important medical events, although they may not result in death, be life-threatening, or require hospitalization may still be considered serious adverse events when, based upon appropriate medical

COVB2710467

judgment, they are felt to jeopardize the subject and may require medical or surgical intervention to prevent one of the outcomes listed above.

Life threatening means that the subject was, in the view of the investigator, at immediate risk of death from the reaction as it occurred. This does not include an adverse event that, if more severe, might have caused death.

Disability means a substantial disruption of a person's ability to conduct normal life's functions.

Serious Adverse Event will be reported to Medtronic-GI Solutions utilizing the electronic case report (Serious Adverse Event CRF eForm) within 24 hours of the investigator's awareness and reported to IRB within 10 working days.

An unanticipated adverse event is any serious, device related adverse event, if that event was not previously identified in the risk analysis and consent form in:

- a. nature
- b. severity or
- c. frequency
- d. Unreasonable risk is not defined. It shall be determined by management on a case-by case basis through evaluation of serious and unanticipated adverse events.

11.2. Reporting of Adverse Events

It is the responsibility of the sponsor to notify all participating investigators of any adverse event associated with the study that is serious or unexpected.

Every adverse event should be recorded in the electronic case report form. Any safety or device deficiency issues which may occur during training with healthy volunteers shall be reported using the Field and Technical report (FTR, form-0021).

The following data must be documented:

- Type of event
- Subject number
- Time of occurrence: date, time
- Time of resolution: date, time
- Severity degree: mild / moderate / severe /
- Relationship to study device: no relationship/possible/probable/definite/unknown
- Measures taken
- Outcome of event: unchanged / worsened / improved / resolved / unknown / death

COVB2710467

Version G 01-DEC-2017

Page 34 of 61

If timely completion of the electronic CRF is not possible, a paper copy can be completed and sent via fax or email GI Solutions at Medtronic [contact] or [contact]. If for any reason the form cannot be completed within 24 hours, a phone call should be made to the sponsor to meet the reporting timeline. In the case of a telephone or faxed/emailed report, sites must still complete the electronic reportable event eCRF at the earliest possible opportunity, and no later than 72 hours following learning of the event.

All other reportable events should be reported within **15 days** of learning of the event. Any safety or device deficiency issues which may occur during training with healthy volunteers shall be reported using the Field and Technical report (FTR, form-0021).

12. Data Review Committees

Data Monitoring Committee (DMC) or Clinical Events Committee (CEC) will not be used for this study.

13. Statistical Design and Methods

For the primary objectives, to assess the acceptability of the Cytosponge in subjects with BE, we will assess the distribution of Impact of Event Scale scores, and the intrusiveness and avoidance subscales. We will generate measures of central tendency and distribution of these data. Bivariate analysis will be performed to assess for predictors of low tolerance of Cytosponge surveillance, and a logistic regression model created to assess these factors while controlling for potential confounders. Data will be compared to population norms in published literature¹ using parametric statistics. VAS scores will be calculated, and measures of central tendency and distribution reported.

Subjects' preferences for Cytosponge versus endoscopic surveillance, as well as willingness to undergo the procedure again, will be measured as proportions, with bivariate and multivariate analyses for predictors of preference performed.

For the second primary objective, to assess the adequacy of samples, sample adequacy will be treated as a dichotomous variable. For purposes of this investigation, an adequate sample will be one in which at least one columnar cell is present. Sample adequacy will be presented as a proportion of subjects who fulfill this definition after up to two total administrations of the Cytosponge, as noted in the methods.

For the first three secondary objectives, to assess the operating characteristics of Cytosponge against various gold standards, initially 2x2 tables will be constructed demonstrating Cytosponge and the gold

COVB2710467

Version G 01-DEC-2017

Page 35 of 61

standard findings (Y/N for BE via endoscopy and Y/N for Intestinal Metaplasia (IM) via biopsies). Both endoscopic evidence of BE and pathological confirmation of specialized IM (intestinal metaplasia with goblet cells) will be used in the final diagnosis of BE. Sensitivity, specificity, positive predictive value, negative predictive value and accuracy will be calculated. Because Cytosponge positivity may vary based on the burden of BE, we will perform sensitivity analyses, defining "positive" cases as those with BE of ≥2 cm in length, and then ≥3 cm in length, to assess impact of disease burden on operating characteristics. Multivariate models controlling for age, sex, burden of disease, and other potential confounders will be constructed, to assess the impact of these factors on test accuracy. Although we do not expect to see an association between the degree of dysplasia and Cytosponge positivity, exploratory analyses will be performed using degree of dysplasia as a predictor variable, and Cytosponge positivity as the outcome variable. For the fourth secondary objective, to assess the degree of mucosal abrasion following Cytosponge, endoscopic abrasion scores will be correlated with the presence of columnar cells on the H&E slide made from the Cytosponge samples.

While the operating characteristics of Cytosponge in our patient population are unknown, the numbers for this post-market study were selected for several reasons. Approximately 50% of the patient population at the involved tertiary care centers have dysplastic BE (25% low-grade dysplasia, 25% high-grade dysplasia), so assessment of 275 patients (with an enrollment ratio of at least \geq 50% BE and \geq 25% GERD) should allow an adequate number of subjects with dysplastic disease to assess performance characteristics with reasonable accuracy. Ten percent of patients with chronic GERD symptoms can be expected to harbor BE, leaving us 75 patients with which to assess specificity, as well as to assess acceptability in patients without disease. For the safety perspective, a sample size of 50 will have greater than 90% probability of detecting a rare event that occurs at a rate of 5%. Results of this study will be used to provide more accurate parameters for power of subsequent studies.

All individuals offered the Cytosponge will be included in analyses of acceptability and adequacy of sampling. All individuals with adequate Cytosponge samples and endoscopy (within 48 hours of Cytosponge) will be included to determine the sensitivity for diagnosis of BE from the TFF3 data (95% confidence intervals will be used).

In an effort to understand the sensitivity and specificity of the test, an interim analysis of the data, based on the statistical methodology outlined above, may be performed after approximately half the study subjects have primary outcomes.

To assess safety (fifth secondary objective), the number and percentage of subjects with adverse events related to Cytosponge administration will be summarized by MedDRA system organ class and preferred term overall, and by severity.

COVB2710467

Version G 01-DEC-2017

Page 36 of 61

14. Ethics

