5.1.2. Secondary Objective(s)

The following 5 secondary objectives will be assessed:

- To assess the operating characteristics of this technique against a gold standard of upper endoscopy with biopsies for endoscopic surveillance in subjects with BE who demonstrate an adequate sample on Cytosponge assessment.
- To assess the operating characteristics of Cytosponge against the worst ever histology documented in the subject. Because Cytosponge provides a "field" sampling of esophageal tissue, it may provide a more comprehensive assessment of minute fields of dysplasia. If this is so, the Cytosponge may avoid sampling error associated with random clinical samples as currently performed. Patients who are undergoing ablative therapy on the day of Cytosponge testing must have biopsies within 2 months prior to treatment.

COVB2710467

Version G 01-DEC-2017

Page 16 of 61

- To assess the operating characteristics of Cytosponge as a function of baseline histology. To date, no data are available regarding the yield of Cytosponge in subjects with BE and more advanced disease (low-grade dysplasia and high-grade dysplasia). These subjects are at greatest risk for progression to cancer. We plan to collect pilot data on operating characteristics of the assay by degree of baseline dysplasia. We hypothesize that Cytosponge will perform with similar operating characteristics in this group compared to non-dysplastic BE.
- To assess the degree of mucosal abrasion following Cytosponge administration, using a standardized scale. Based on previous data, we hypothesize that mucosal damage due to abrasion by the Cytosponge will be minor. Further, the distal extent of the abrasion will correlate with the presence of columnar cells in the sample.
- To collect and analyze ongoing safety measures of Cytosponge use in the target population. The Cytosponge has been found to be safe and well-tolerated when administered in a primary care setting. We will continue collecting safety data as part of this project. All AEs will be coded using MedDRA.

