Appendix I: Cytosponge Abrasion Scale

Grading of Cytosponge abrasions for US Pilot Cytosponge Study

The most distal level (depth of insertion of endoscopy from teeth) of the Cytosponge abrasions should be recorded; this is best seen on initial intubation of the esophagus and stomach. The grading of Cytosponge abrasion is shown below:

Grade 1. One or more abrasions, less than 5mm with no oozing of blood

Grade 2. One or more abrasions, more than 5mm with no oozing of blood

Grade 3. One or more abrasions with no active bleeding but minimal ooze of blood not compromising mucosal views

Grade 4. One or more abrasions with no active bleeding but some ooze of blood making it difficult to visualise the mucosa clearly

Grade 5. One or more abrasions resulting in active bleeding requiring endoscopic or surgical intervention.

Grade 5 abrasions should be considered serious adverse events and reported to the sponsor immediately per the protocol. All other abrasions should be considered adverse events and

CASE II Clinical Investigation Plan					
COVB2710467	Version G	01-DEC-2017	Page 44 of 61		Medtronic

reported per the protocol.

Sponsor contacts:

COVB2710467

Version G 01-DEC-2017

Page 45 of 61

Medtronic

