6.6.1.1.2 Secondary Objectives

6.6.1.1.3 Secondary Objective 1

To assess the operating characteristics of Cytosponge against a gold standard of upper endoscopy with biopsies for endoscopic surveillance in subjects with BE who demonstrate an adequate sample on Cytosponge assessment. It is expected that the assay will demonstrate both a sensitivity and specificity of > 90% in the detection of BE. Further, we expect higher accuracy in those with a larger burden of disease.

6.6.1.1.4 Secondary Objective 2

[figure not shown]
To assess the operating characteristics of Cytosponge against the worst ever histology documented in the subject.

6.6.1.1.5 Secondary Objective 3

To assess the operating characteristics of Cytosponge as a function of baseline histology. To date, no data are available regarding the yield of Cytosponge in Subjects with BE and more advanced disease (low-grade dysplasia and high-grade dysplasia). These subjects are at greatest risk for progression to cancer. We plan to collect pilot data on operating characteristics of the assay by degree of baseline dysplasia. It is expected that Cytosponge will perform with similar operating characteristics in this group compared to non-dysplastic BE.

For the secondary objective 1, 2 and 3, to assess the operating characteristics of Cytosponge against various gold standards, two-by-two tables will be constructed demonstrating Cytosponge and the gold standard findings (Y/N for BE). Sensitivity, specificity, positive predictive value, negative predictive value and accuracy will be calculated.

Revision 2.0

Page 13 of 13

6.6.1.1.6 Secondary Objective 4

To assess the degree of mucosal abrasion following Cytosponge administration, endoscopic abrasion score, a standardized scale, will be calculated. The distal extend of cells collected by recording the location of abrasions as well as their grade. Based on previous data, it is expected that mucosal damage due to abrasion by the Cytosponge will be minor. Further, the distal extent of the abrasion will correlate with the presence of columnar cells on the H&E slide made from Cytosponge samples in the sample.

6.6.1.1.7 Secondary Objective 5

To assess safety, the number and percentage of subjects with adverse events (AEs) related to Cytosponge administration will be summarized by MedDRA system organ class and preferred term overall, and by severity.

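### The distal-extent hypothesis of secondary objective 4 has no matching analysis: the protocol correlates abrasion grade, and the SAP names distal extent without a method

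*Protocol*

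**What the plan says.** Protocol 5.1.2 and the synopsis, repeated in SAP section 4, give objective 4 three parts.

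- The aim: "To assess the degree of mucosal abrasion following Cytosponge administration, using a standardized scale".
- A first hypothesis about severity: "we hypothesize that mucosal damage due to abrasion by the Cytosponge will be minor".
- A second hypothesis about location: "Further, the distal extent of the abrasion will correlate with the presence of columnar cells in the sample".

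Protocol section 13 gives one analysis for the objective: "endoscopic abrasion scores will be correlated with the presence of columnar cells", as seen on the H&E slide of the sponge sample. The synopsis and SAP section 4 carry the same sentence.

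Appendix I of the protocol asks for two items. One is a grade from 1 to 5. The other is a position: "The most distal level (depth of insertion of endoscopy from teeth) of the Cytosponge abrasions should be recorded".

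SAP 6.6.1.1.6 says that an "endoscopic abrasion score, a standardized scale, will be calculated". It follows this with an incomplete sentence about recording the location of abrasions along with their grade, and then restates the expected link between distal extent and columnar cells.

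**The concern.** The hypothesis asks whether a sponge that abraded further down was more likely to bring back columnar cells. The grade describes how large an abrasion is and how much it oozes or bleeds. Any relation between grade and depth would be incidental, so the correlation in section 13 can come out null or positive whether or not the hypothesis is true.

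The SAP does not settle the matter. An analyst working from its section 4 would correlate the score. One working from 6.6.1.1.6 might use distal extent, but would have to invent the method. At stake is whether the trial can report on its own stated hypothesis with data that Appendix I already requires.

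**Working it through.** The documents state no alpha, power, effect size or sample size for objective 4, so there is no figure to reproduce. The check sets the texts side by side.

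**1. Hypothesis against analysis variable**

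| Item | Source | Content |
|---|---|---|
| Hypothesis 1 | Protocol 5.1.2 | Severity of abrasion |
| Hypothesis 2 | Protocol 5.1.2 | Distal extent against columnar cells |
| Planned correlation | Protocol 13; synopsis; SAP 4 | Score against columnar cells |
| Score | Appendix I | Grades 1–2: size, no oozing; 3–4: oozing; 5: active bleeding needing intervention |
| Distal level | Appendix I | Separate item, depth from the teeth |
| SAP method for hypothesis 2 | SAP 6.6.1.1.6 | Expectation only |

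No grade refers to position. Take one subject with a proximal Grade 3 abrasion and another with a distal Grade 1 abrasion. The score ranks the first above the second; distal extent ranks them the other way round. The score cannot stand in for the variable in hypothesis 2.

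**2. Which sample goes with which abrasion**

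Abrasions are graded at the study endoscopy (protocol 9.5). After an inadequate first sample only the sponge is repeated, not the endoscopy (protocol 6.1 and footnote 1 of 9.1). Only the first-sponge sample therefore has abrasion data from the same administration. Objective 4 does not say which sample is meant.

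**3. Subjects with no abrasion**

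The scale starts at Grade 1, which already requires at least one abrasion. Neither document says how a subject with none enters the analysis. Such a subject has no distal level either.

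**4. Reference point**

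Depth from the teeth reflects both the subject's anatomy and the position of the abrasion relative to the junction. Neither document says whether it is to be related to the junction or to the top of the gastric folds. The arms also differ. BE subjects enter with a columnar segment of C1 or more, or M3 or more, so the sponge can meet columnar lining well above the folds.

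**5. How many subjects would lack columnar cells**

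The documents give no first-sponge adequacy rate, so 80%, 90% and 95% are assumptions. Expected number without columnar cells = N × (1 − adequacy). The N used are the maximum enrolment of 275 and the minimum arm shares of 50% (137.5) and 25% (68.75).

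| Assumed adequacy | All, 275 | BE, 137.5 | GERD, 68.75 |
|---|---|---|---|
| 80% | 55.0 | 27.5 | 13.8 |
| 90% | 27.5 | 13.8 | 6.9 |
| 95% | 13.8 | 6.9 | 3.4 |

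The remaining 25% of enrolment could raise either arm. Smaller total enrolment, failures to swallow and subjects with no abrasion would lower these counts. A corrected analysis may therefore give wide intervals, most of all within arms.

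**The case against.** The strongest reply is that this is a specification gap with little consequence. The grade answers the objective's lead sentence and its first hypothesis. The SAP does not drop distal extent: 6.6.1.1.6 says location is recorded and pairs it with columnar cells on the H&E slide. The study is a pilot, nothing is decided on this result, and section 6 of the protocol says that results will not influence patient management.

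Most of this stands, and it limits the point. It does not remove it, because the one correlation the plan does specify uses a variable that cannot address the hypothesis.

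Three stronger readings are tempting, and the documents do not support them.

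- A reader might infer that objective 4 as a whole goes untested. It does not; only its second hypothesis lacks an analysis.
- A reader might infer that recording depth from the teeth defeats the analysis, or try to put a percentage on the loss. Appendix I says how the level is recorded, not that unadjusted depth is the analysis variable. The documents give no standard deviations from which a loss could be calculated. Such a measure would dilute an association, not prevent its estimation.
- A reader might infer that second-sponge samples will be paired with first-sponge abrasions. The rule allowing up to two administrations belongs to primary objective 2. Objective 4 is silent, and pairing with the first sample is the natural reading. One clarifying phrase is enough.

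**Conclusion.** The concern holds in a limited form. The distal-extent hypothesis of objective 4 has no matching analysis. Protocol section 13 and SAP section 4 correlate a grade of size and bleeding, and SAP 6.6.1.1.6 names distal extent without a method. The grade remains the right variable for the main aim and the minor-damage hypothesis.

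The reach is one of two hypotheses under one of five secondary objectives. No primary result is affected. No numerical size can be given from the documents, and the conclusion needs none: it rests only on the definitions in Appendix I and the wording of the analysis sentences. The counts of subjects without columnar cells rest on assumed adequacy rates and bear only on the precision of the corrected analysis. The change is worth making because it costs little and lets the trial address a hypothesis it has stated.

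**What to change.** In protocol section 13 and SAP 6.6.1.1.6, and in the matching sentences of the synopsis and SAP section 4, replace the score correlation for this hypothesis as follows.

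- **Variables.** Relate the most distal abrasion level, already recorded under Appendix I, to presence of columnar cells (yes/no) in the first-sponge sample only.
- **Estimate.** Compare distal level between samples with and without columnar cells, with a 95% CI, separately for the BE and GERD arms.
- **Reference level.** Where the CRF holds it, express the level relative to the top of the gastric folds or the junction. In the BE arm, also express it relative to the proximal margin of the columnar segment. Otherwise use depth from the teeth and state that this dilutes the association.
- **No abrasion.** State that these subjects have no distal level and report them as a separate category.
- **Grade.** Report it descriptively, for the main aim and the minor-damage hypothesis.

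The cost is wording, plus a check of which reference levels the CRF captures. No new procedure is needed. The downside is precision: the group without columnar cells may be small, so the intervals may be wide and the result should be presented as exploratory.
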